6.2.3.2 Follow-up visit

Additional follow-up visits after the 90-day safety follow-up visit will only be performed for patients who did not progress on treatment to monitor tumour progression and safety. These will be performed once every 12 weeks at least (by telephone or in person) until PD, introduction of a new anti-cancer treatment, death, loss to follow-up, withdrawal of consent, or for a maximum of 6 months after EoT.

7. STATISTICAL METHODS AND DETERMINATION OF SAMPLE SIZE

This trial will be performed as an open-label trial. The primary objectives of this trial are to determine the MTD and/or the RD-P2 of BI 1387446 as monotherapy in superficial lesions (Arm A) and to determine the MTD and/or the RD-P2 of BI 1387446 in combination with ezabenlimab (BI 754091) in superficial lesions (Arm B). To determine the MTDs, patients are entered sequentially into escalating dose cohorts (see [Section 3](#)).

The dose escalation will be guided by a Bayesian 5-parameter logistic regression model with overdose control [[R15-4233](#)] using a hierarchical modelling approach to jointly model both arms and taking into account data available for ezabenlimab (BI 754091) from the ongoing trial 1381-0001. Trial 1381-0001 is also an oncology dose finding trial which comprises a similarly heterogeneous population of patients with solid tumours. A comparison between trial 1426-0001 and 1381-0001 regarding study population, DLT definition and treatment schedule is presented in [Appendix Table 10. 5: 3](#). A visualisation of the joint-modelling approach is given in [Figure 7: 1](#).

[figure not shown]

Figure 7: 1 Joint BLRM modelling approach for Arms A and B

The logistic regression model for Arm A and B is defined as follows. Let $\pi_{1,d1}$ be the probability of having a DLT when giving dose d_1 of BI 1387446 as monotherapy, and $\pi_{2,d2}$ the probability of having a DLT when giving dose d_2 of the combination partner ezabenlimab (BI 754091) as monotherapy, respectively. A logistic regression is used to model the dose-toxicity relationship for each of these drugs individually:

$$\text{BI 1387446: } \text{logit}(\pi_{1,d1}) = \log(\alpha_1) + \beta_1 \log(d_1/d_1^*)$$

$$\text{Ezabenlimab (BI 754091): } \text{logit}(\pi_{2,d2}) = \log(\alpha_2) + \beta_2 \log(d_2/d_2^*)$$

Here, the doses d_1 and $d_2^* = 240$ mg represent the reference doses for BI 1387446 and ezabenlimab (BI 754091), respectively.

Assuming no toxicity interaction between the two compounds, the probability of a DLT when giving the combination dose d_1, d_2 is obtained as

$$\pi_{12,d1,d2}^0 = \pi_{1,d1} + \pi_{2,d2} - \pi_{1,d1}\pi_{2,d2}$$

with corresponding odds

$$\text{odds}(\pi_{12,d1,d2}^0) = \pi_{12,d1,d2}^0 / (1 - \pi_{12,d1,d2}^0)$$

In order to account for a potential positive (higher toxicity than expected under independence) or negative (lower toxicity than expected under independence) interaction between BI 1387446 and ezabenlimab (BI 754091), a dose-dependent interaction term $-\infty < \eta < \infty$ is introduced in the model by the following definition:

$$\text{odds}(\pi_{12,d1,d2}) = \text{odds}(\pi_{12,d1,d2}^0) \exp(\eta d_1/d_1^* d_2/d_2^*)$$

and $\pi_{12,d1,d2}$ is used in the likelihood

$$r_{d1,d2} \sim \text{Binomial}(n_{d1,d2}, \pi_{12,d1,d2})$$

where $r_{d1,d2}$ denotes the random variable describing the observed number of DLTs in $n_{d1,d2}$ patients at the dose combination d_1, d_2 .

The joint analysis of the dose escalation Arms A and B of this trial and the information available from trial 1381-0001 follows a normal-normal hierarchical model with 3 parameter models:

- 1) A multi-variate normal distribution for BI 1387446 as single agent:
 $\theta_{1,j} = (\log(\alpha_{1,j}), \log(\beta_{1,j})) \sim N((\mu_{\alpha_1}, \mu_{\beta_1}), \Psi_1), j = 1, \dots, 3$
- 2) A multi-variate normal distribution for ezabenlimab (BI 754091) as single agent:
 $\theta_{2,j} = (\log(\alpha_{2,j}), \log(\beta_{2,j})) \sim N((\mu_{\alpha_2}, \mu_{\beta_2}), \Psi_2), j = 1, \dots, 3$
- 3) A normal distribution for the interaction parameters η_j :
 $\eta_j \sim N(\mu_\eta, \tau_\eta^2), j = 1, \dots, 3$

The parameters $\theta_{1,j}$, $\theta_{2,j}$, and η_j are the corresponding trial-specific parameters of each trial-specific BLRM (for trials $j=1,2,3$). The covariance matrices Ψ_i ($i=1,2$) are assumed to be of the form

$$\Psi_i = \begin{pmatrix} \tau_{\alpha_i}^2 & \rho_i \tau_{\alpha_i} \tau_{\beta_i} \\ \rho_i \tau_{\alpha_i} \tau_{\beta_i} & \tau_{\beta_i}^2 \end{pmatrix}$$

For this hierarchical model, the monotherapy dose-finding in Arm A and the double combination therapy dose-finding in Arm B, and trial 1381-0001 are assumed to be separate trials, with different inter-study random effects $\tau_{\alpha_1}, \tau_{\beta_1}, \tau_{\alpha_2}, \tau_{\beta_2}, \tau_\eta$ for the involved parameters. The parameters $\log(\alpha_{i,j})$ and $\log(\beta_{i,j})$ ($i=1,2$; $j=1,2,3$) are assumed to be potentially correlated with correlation coefficients ρ_i , $i=1, 2$, while the remaining parameters are assumed to be uncorrelated. Refer to [\[R18-3210\]](#) for details.

Since a Bayesian approach is applied, prior distributions f for each of the parameters $\mu_{\alpha_1}, \mu_{\beta_1}, \mu_{\alpha_2}, \mu_{\beta_2}, \mu_\eta, \tau_{\alpha_1}, \tau_{\beta_1}, \tau_{\alpha_2}, \tau_{\beta_2}, \tau_\eta$ and for ρ_1 , and ρ_2 need to be specified. Weakly informative prior distributions were chosen for the μ - and ρ -parameters, prior distributions for the τ -parameters are chosen to represent a small to moderate between-trial heterogeneity (see [Table 7: 1](#)).

Table 7: 1

Prior parameters of the joint model for Arms A and B

Parameter	Prior distribution
μ_{α_1}	N(log(0.5),2)
μ_{β_1}	N(0,1)
μ_{α_2}	N(log(0.5),2)
μ_{β_2}	N(0,1)
μ_{η}	N(0,1)
τ_{α_1}	logN(log(0.25),log(2)/1.96)
τ_{β_1}	logN(log(0.125),log(2)/1.96)
τ_{α_2}	logN(log(0.25),log(2)/1.96)
τ_{β_2}	logN(log(0.125),log(2)/1.96)
τ_{η}	logN(log(0.125),log(2)/1.96)
ρ_1	U(-1,1)
ρ_2	U(-1,1)

The toxicity probabilities $\pi_{1,d1}$, and $\pi_{12,d1,d2}$, of a DLT at each dose/dose combination will be calculated directly from the posterior samples regarding the arm-specific parameters, i.e. including the respective arm-specific random effects per parameter. They will be summarized per arm using the following intervals:

Under toxicity: [0.00, 0.16)

Targeted toxicity: [0.16, 0.33)

Overtotoxicity: [0.33, 1.00]

Prior probabilities of DLTs at different dose levels/dose combinations, as well as the corresponding probability of under-, targeted and overtotoxicity, are shown in [Table 7: 2](#) and [Table 7: 3](#) for the initial weakly informative priors of the joint model for Arms A and B. As can be seen from these tables, the prior medians of the DLT probabilities represent reasonable assumptions on toxicity, and the uncertainty around the medians is large, showing the low amount of information this prior provides.

Prior probabilities in Arm A show that [REDACTED] fulfils the EWOC criterion and is therefore a suitable starting dose for the monotherapy dose finding in superficial lesions. Prior probabilities for Arm B do not allow to start combination dose finding at [REDACTED] without additional data. However, from the data scenarios provided in [Section 10.5](#) and from

[Tables 7: 4](#) and [7: 5](#), it can be seen that with some additional data from the monotherapy dose finding trials, the overdose probabilities decrease [REDACTED] becomes a suitable starting dose. Of note: At time of amending the CTP to version 5.0, Arm B was already started at this dose level.

Table 7: 2 Prior probabilities of DLTs in Arm A

[REDACTED]								
	[REDACTED]							
[REDACTED]								
[REDACTED]								
[REDACTED]								
[REDACTED]								
[REDACTED]								
[REDACTED]								
[REDACTED]								

Table 7: 3 Prior probabilities of DLTs in Arm B

[REDACTED]								
	[REDACTED]							
[REDACTED]								
[REDACTED]								
[REDACTED]								
[REDACTED]								
[REDACTED]								
[REDACTED]								
[REDACTED]								

In addition, [Tables 7: 4](#) and [7: 5](#) show the prior probabilities for Arm A and B taking into account data from 1381-0001 that has already been obtained by the time of the CTP writing of this trial. The following data from 1381-0001 has been included in the calculations for the tables given below:

Since this data will be included in all BLRM analyses, the prior probabilities given in [Table 7: 2](#) and [Table 7: 3](#) are not used in practice but only the ones shown in the below tables.

Table 7: 4

Prior probabilities of DLTs in Arm A (taking into account data from 1381-0001)

Table 7: 5

Prior probabilities of DLTs in Arm B (taking into account data from 1381-0001)

The BLRM-recommended dose combination for the next cohort is the level with the highest posterior probability of the DLT rate falling in the target interval [0.16, 0.33) among the doses or dose combinations fulfilling the EWOC principle. Per EWOC it should be unlikely (<25% posterior probability) that the DLT rate at the dose combination will exceed 0.33. However, the maximum allowable dose increment for the subsequent cohort will be no more than 100% for each drug.

The MTD may be considered reached in each arm separately if all of the following criteria are fulfilled:

- Next recommended dose by the BLRM = current dose.

- At least 12 patients have been treated in the specific arm.

And at least one of the following criteria is fulfilled:

- The posterior probability of the true DLT rate in the target interval [0.16 – 0.33) of the MTD is above 0.50, OR
- At least 6 patients have been treated at the MTD.

A detailed evaluation of the model using hypothetical data scenarios and operating characteristics is provided in the statistical appendix ([Section 10.5](#)).

The dose finding part of the trial will be analysed once using the hierarchical model described above. A sensitivity analysis of the dose finding part will consist of separate analyses of each dose finding arm using weakly informative priors for each arm.

7.1 NULL AND ALTERNATIVE HYPOTHESES

No confirmatory testing is performed and hence no null and alternative hypotheses are defined. A justification of the sample size is provided in [Section 7.5](#).

7.2 PLANNED ANALYSES

7.2.1 General considerations

For the determination of the MTD, only MTD evaluable patients will be considered. For the analysis of all other endpoints, all patients in the treated set (i.e. patients treated with at least one dose of trial medication) will be included in the analysis. Analyses will in general be performed by initial treatment, with the exception of patients who cross over from Arm A to Arm B. These patients will be analysed as part of Arm A as long as they are treated with monotherapy and as part of Arm B when they are treated with combination therapy.

More details and all other patient analysis sets will be defined in the Trial Statistical Analysis Plan (TSAP).

No per protocol set will be used in the analysis. However, important protocol deviations will be summarized.

7.2.2 Primary endpoint analyses

In order to identify the MTD, the number of evaluable patients with DLTs during the MTD evaluation period at each dose level in each arm must be presented. Replaced patients will be excluded from the determination of MTD.

For Arm A and B, the main analysis of the MTD will use the joint 5-parameter BLRM model described above using DLT data from the MTD evaluation period. For this analysis, cross-over patients will only be included while being treated with BI 1387446 monotherapy in Arm A.

The following sensitivity analyses for the analysis of the MTD will be performed to support the determination of the RD-P2:

[figure not shown]
- Separate BLRMs will be used for each escalation arm using all DLT data, not only DLT data from the MTD evaluation period
- The joint BRLM will be evaluated using all DLT data, not only DLT data from the MTD evaluation period

The sensitivity analyses will include all treated patients, including 'backfill' patients and cross-over patients. More details on sensitivity analyses will be specified in the TSAP.

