Statistical methods	Descriptive statistics will be used for all analyses. Dose escalation will be guided by a Bayesian logistic regression model (BLRM) with overdose control that will be fitted to binary toxicity outcomes using a hierarchical modelling approach to jointly model escalation arms A and B. The estimates of the model parameters will be updated as data are accumulating using the BLM. At the end of the dose escalation the toxicity probability at each dose level in each arm will be calculated to determine an estimate of the MTD in each arm.

Proprietary confidential information © 2023 Boehringer Ingelheim International GmbH or one or more of its affiliated companies

FLOW CHART: OVERVIEW-ARM A AND ARM B

Trial Periods	Screening	Treatment period ¹												Post treatment period			
		Cycle 1			Cycle 2			Cycle 3			Cycle 4		Cycle 5	Cycle 6-34	End of treatment	30-Day Safety Follow-up	90-Day Safety Follow-up
Visit	Screening	C1 V1	C1 V2	C1 V3	C2 V1	C2 V2	C2 V3	C3 V1	C3 V2	C3 V3	C4V1	C5V1	C6V1 – C34V1	EoT ³	30dFU ³	90dFU ³	EoTria 1
Days													1		EoT+ 30 days	EoT+ 90 days	
Time window for visits (day)					+1	+1	+1	+1	+1	+1	+3	±3	±3	+ 7	+ 7	+ 14	
Overnight stay ⁴		X		X													
Informed consent ⁵	X																
Demographics ⁶	X																
Medical history ⁶	X																
Physical examination ⁶	X	X	X ³⁰	X ³⁰	X	X ³⁰	X ³⁰	X	X ³⁰	X ³⁰	X	X	X ³⁰	X	X		
Vital signs ⁶	X	X	X	X	X	X	X	X	X	X	X	X	X	X			
ECOG Performance Status ⁶	X	X			X			X				X	X ³¹	X	X		
Safety laboratory tests ^{6, 7, 8}	X ⁹	X ³²	X ⁹	X ⁹	X	X ⁹	X ⁹	X	X ⁹	X ⁹	X	X	X	X			
12-lead ECG (single/triplicate) ¹⁰	X	X			X			X				X	X ¹¹	X	X ¹²		
Echocardiography (or MUGA) ³⁷	X				X ³⁴						X ³⁴		X ³⁴	X			
Review of in-/exclusion criteria	X	X															
Allocation to treatment	X																
PK blood sampling for BI 1387446 ¹⁷		X	X	X	X	X	X	X	X	X	X	X	X	X ¹⁶			
PK blood sampling for ezabenlimab (BI 754091) ^{14, 17}		X	X	X	X	X	X	X			X	X	X	X ¹⁶			
Anti-drug antibodies (ADAs) blood sampling ^{14, 17}		X			X			X					X ²⁹	X ¹⁶			

Proprietary confidential information © 2023 Boehringer Ingelheim International GmbH or one or more of its affiliated companies

FLOW CHART: OVERVIEW-ARM A and ARM B (cont.)

Trial Periods	Screening	Treatment period ¹										Post treatment period					
		Cycle 1			Cycle 2			Cycle 3			Cycle 4	Cycle 5	Cycle 6-34	End of treatment	30-Day Safety Follow-up	90-Day Safety Follow-up	Follow-up ²

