The frequency, time to onset, and severity of toxicities, as well as the success of standard medical management and dosing interruptions/delays, will be analysed to determine if a given toxicity not listed above should be considered a DLT for dose escalation purposes.

Late DLTs are AEs that meet the DLT criteria but occur on treatment after the completion of the initial MTD evaluation period (Arm A and B: Cycle 1, including echocardiographic/MUGA scan measurements acquired on Day 1 of Cycle 2 and related findings). If any late DLT is reported during dose escalation, the BLRM will be rerun using all DLTs, and updated results will be reviewed in the SMC meeting to recommend the next dose level and cohort size.

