## 7.4.4 Supplementary analysis

As a supplementary analysis, the joint BLRM may be analyzed using DLT data from the whole on-treatment period instead of DLT data from the MTD evaluation period. This analysis will include all treated patients, including 'backfill' patients and cross-over patients.

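### The all-DLT BLRM mixes dose with time on treatment and counts early leavers as DLT-free, so its overdose probabilities cannot be read against the cycle 1 limits of 0.16 and 0.33

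*Protocol*

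**What the plan says.** The main MTD analysis uses DLTs from the MTD evaluation period (cycle 1, 3 weeks, plus the cycle 2 day 1 echo/MUGA) in evaluable patients only (Protocol 7.2.2, SAP 6.4 and 7.4.1).

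To support the RD-P2, Protocol 7.2.2 adds sensitivity analyses, both arm by arm and jointly. For the joint model: "The joint BRLM will be evaluated using all DLT data, not only DLT data from the MTD evaluation period". On the patient set: "The sensitivity analyses will include all treated patients, including 'backfill' patients and cross-over patients". SAP 7.4.4 retains only the joint version and makes it optional: "the joint BLRM may be analyzed using DLT data from the whole on-treatment period instead of DLT data from the MTD evaluation period". SAP 6.1 ends the on-treatment period 90 days after the last dose and gives a cross-over patient one such period in each arm.

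A similar refit occurs during escalation. After a late DLT, Protocol 4.1.4.4 says "the BLRM will be rerun using all DLTs, and updated results will be reviewed in the SMC meeting to recommend the next dose level" and the cohort size. It does not say which patients enter.

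The model is described in the synopsis as "fitted to binary toxicity outcomes using a hierarchical modelling approach". In Protocol Section 7 the likelihood is Binomial(n, π) at each dose, where r "denotes the random variable describing the observed number of DLTs in" n patients. There is no term for cycles or time at risk. The only limits are 0.16 and 0.33 with the 25% EWOC rule, and SAP 7.4.1 ties the 33%/25% rule to the MTD evaluation period. Neither the protocol nor SAP 7.4.4 gives a minimum follow-up, a censoring rule or other limits for the all-DLT runs.

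**The concern.** A DLT rate over 3 weeks and a DLT rate over a patient's whole time on trial are different quantities. BI 1387446 may be given for 18 cycles, or up to 34 with a partial response; ezabenlimab may be given for 34 (Protocol 4.1.2.3). Three things follow when all of this is collapsed into one yes/no outcome.

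- **Upward shift.** Longer follow-up raises the event rate at any dose, so a dose can look too toxic because its patients stayed on treatment.
- **Downward shift.** Protocol 3.3.4.4 removes from the MTD determination patients who leave cycle 1 for a reason other than a DLT. Taking all treated patients puts them back as full non-events, so a dose can look safer than it is.
- **Double contribution.** A cross-over patient supplies an outcome in each arm. The Arm B outcome comes from someone who had already completed cycle 1 of BI 1387446.

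If the all-DLT result differs from the main analysis, the reader cannot tell whether dose, follow-up or the patient set caused it. Yet the result is meant to inform the RD-P2, and the 4.1.4.4 rerun informs the next dose level.

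**Working it through.** **Inputs from the documents:** the Table 7: 1 priors for BI 1387446, the 0.16/0.33 intervals, EWOC as P(π ≥ 0.33) < 0.25, and the scenario 02 result in Protocol 10.5.

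**Assumed:** the second argument of each normal prior is an SD; the redacted reference dose d* is 800 µg unless varied; steps 4 to 6 use five doubling doses up to 800 µg. Only the monotherapy part is fitted: logit(π) = log α + β log(d/d*).

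**1. Check against the plan's own figure.** One DLT in one patient at 50 µg gives P(overdose) = 0.656 at d* = 800 µg, equal to the protocol's 0.656. Over d* from 200 to 3200 µg it runs from 0.714 to 0.620. The implementation is compatible with the plan, but this is not an independent reproduction, because d* is unknown.

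**2. Cumulative risk.** With a constant risk p per cycle, the ever-DLT rate after k cycles is 1 − (1 − p)^k. For p = 0.05:
- k = 1: 0.050
- k = 6: 1 − 0.95^6 = 0.265
- k = 8: 1 − 0.95^8 = 0.337
- k = 18: 1 − 0.95^18 = 0.603

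A cycle 1 rate far below 0.16 passes 0.33 at 8 cycles.

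**3. Follow-up alone, through the BLRM.** Six doses from 1/32 to 1 times d*, 6+6+6+6+6+4 = 34 patients (the Arm A plan), a flat 5% per cycle at every dose, expected counts. At the top dose P(overdose) is 0.038, 0.204, 0.673 and 0.885 for 1, 3, 6 and 8 cycles. Every dose passes EWOC at 1 cycle. At 8 cycles only the two lowest pass (0.120 and 0.215).

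**4. Simulation.** 300 trials, 6 patients at each of five doses, per-cycle risks 1, 2, 3, 5 and 8%, mean 4 cycles.

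| Later per-cycle risk as share of cycle 1 | Top dose fails EWOC, ever-DLT data |
|---|---|
| 100% | about 57% to 62% |
| 25% | about 20% |
| 10% | about 10% |

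With cycle 1 data it fails in 7% to 9%. The simulation error at 60% is √(0.6 × 0.4 / 300) = 0.028, about 3 points. The size therefore depends strongly on the late hazard.

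**5. Dose still counts.** With equal mean follow-up and constant risk, the simulated ever-DLT rate rises from about 3% at the lowest dose to 26% at the highest. Only if mean follow-up is set to 10, 8, 6, 4 and 2 cycles from lowest to highest dose does the gradient nearly vanish (9, 16, 16, 18 and 14%).

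**6. Dilution.** With 0/3 at each of four lower doses, 2 DLTs in 6 evaluable patients at the top dose give P(overdose) = 0.31, which fails EWOC. Adding two early leavers makes it 2/8 and 0.18, which passes. At d* = 1600 µg the values are 0.19 and 0.10, and both pass. The fall is there in each case, but whether it crosses 0.25 depends on the redacted reference dose.

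**The case against.** The strongest reply is that this is a secondary look. Cycle 1 DLTs in evaluable patients define the MTD; Protocol 4.1.4.4 says that only first-cycle DLTs are required for escalation decisions; the SMC weighs model output with other clinical information; SAP 7.4.4 makes the analysis optional; and SAP Section 4 records that development has ended. Asking how often a DLT ever occurs is also a legitimate question. All of this stands and limits the weight of the point. It does not remove it, because Protocol 7.2.2 assigns these runs to the RD-P2 and 4.1.4.4 makes the rerun mandatory after a late DLT.

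A reader might infer more than the documents support:

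- **That the output reflects time on treatment instead of dose.** It does not: the dose term remains, and step 5 shows the rate rising with dose under equal follow-up. A pattern of longer follow-up at lower doses is possible but not assured, since backfill adds later patients there (Protocol 3.1.2).
- **That early-leaver dilution and cross-over double counting enter next-dose decisions.** All treated patients are named only in 7.2.2 and SAP 7.4.4. If the 4.1.4.4 rerun keeps evaluable patients, late DLTs over a fixed denominator move the result only towards caution.
- **That the plan states it will apply the cycle 1 limits to the all-DLT run.** This is inferred, because the same model is rerun and no other limits are given.

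A constant hazard has no source in the documents, and visits become less frequent from cycle 4. Hence the range in step 4.

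**Conclusion.** The point holds in this form: the all-DLT BLRMs in Protocol 7.2.2 and SAP 7.4.4 mix dose with time on treatment, can err in either direction, and cannot be read against 0.16 and 0.33. The 4.1.4.4 rerun shares the unequal follow-up; its patient set is not stated, so dilution and double counting are not shown there. The main MTD analysis is unaffected.

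The size is uncertain. EWOC failure at the top dose ranges from about 57% to 62% under constant risk down to about 10%, close to the 7% to 9% seen with cycle 1 data, when later risk is a tenth of cycle 1 risk. These figures rest on the assumed 800 µg reference dose, priors read as SDs, a mean of 4 cycles and invented per-cycle risks. The structural defect needs none of these assumptions. It is worth correcting because one of the biases can make a dose look safer than it is.

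**What to change.** 1. In Protocol 7.2.2 and SAP 7.4.4, count a patient without a DLT only if he or she completed the MTD evaluation period. State that the 4.1.4.4 rerun uses the same evaluable set.
2. Keep the all-DLT run, but add a companion version adjusted for exposure. This can be a common fixed window, counting patients with a DLT in it or observed to its end, or a model of risk per cycle (complementary log-log link, log cycles at risk as offset). Read only a result on the 3-week scale against 0.16 and 0.33.
3. Show Arm B with and without cross-over patients, and list late DLTs by dose with cycles at risk.

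**Cost:** wording in both documents and modest extra Stan code; no new data. A few patients leave the sensitivity set. The per-cycle version assumes a constant hazard, and a fixed window omits later DLTs from that run, which is why the all-DLT run and the listing should stay beside it.
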